PROCEDURES	
One selected site that is experienced in the treatment of pediatric and adult patients with bone deformities and fractures, where the usage of JPS is already part of the normal clinical practice, will participate in this study. Investigator will provide data for a maximum of 40 JPS implant cases satisfying inclusion and exclusion criteria (predicted drop out rate is 10%) that will contribute for at least 30 cases treated by JPS (note that some patients may contribute for more than one JPS case, according to how many JPS implants were received).
 
For retrospective study cohort, who has previously had JPS implanted and follow-up assessment and JPS removal is done, the investigators shall purely collect clinical data from the medical record of the subjects, concerning the screening criteria, the surgery (MD application) and 4 following events: hospital discharge, first post-application control, bone consolidation assessment and device removal. Data from patients' observation are collected according to the site standard-of-care.
 
Patients, who are prospectively enrolled in the study and have undergone JPS implantation, will have follow-up assessments, as described on Table 10.2, or until patient withdrawal.

[figure not shown]
	
The patient data will be systematically collected by the investigator in eCRF. As per CIP, the subjects will not undergo additional visit nor non-invasive, invasive or burdensome procedures additional to those performed under the normal clinical practice.
					
OBJECTIVES	
The objectives of this study are to assess:
 
 - the safety profile (primary objective) - the clinical performance (secondary objective) 
of the JPS within the scope of its intended purpose, when used according to the manufacturer IFU on a representative population of subjects and users.
					
SAFETY ENDPOINTS	
The safety profile of JPS will be assessed by the following safety endpoints:
 
 - Percentage (%) of subjects with at least one serious/not serious adverse event certainly related or possibly related to JPS (ADEs) (primary safety endpoint) at device removal follow-up (up to 18 months according to site's standard practice); - Percentage (%) of MD Deficiencies (MDDs) at device removal follow-up (up to 18 months according to site's standard practice). 					

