STATISTICAL METHODOLOGY	
Hypothesis to test: the observed primary safety endpoint for JPS ranges within the state-of-art (SOA) safety profile of equivalent plating systems.
 
Primary safety endpoint: the proportion of subjects (% \pm the upper and lower limit of the 95 % confidence interval) with at least one serious/not serious adverse event surely or possibly related to JPS.
 
State of art: The proportion of subjects with serious/not serious adverse event related or possibly related to the device reported in the scientific literature for the treatment of congenital deformities and fractures in lower limb of pediatric and appropriate adult patients by the means of equivalent plating systems is between 5.1 % and 15.0 % depending on many factors, mainly the diversity of the primary diagnosis.
 
Assumption: for the sole purpose of the sample size calculation, it was required to assume an expected proportion of subjects for the primary safety endpoint of JPS. The sample size, therefore, was calculated estimating the required number of subjects so that the upper limit of the 95% confidence interval for the expected proportion is ranged within the SOA (i.e. 95% CI upper limit \leq 15 %).

	
Sample size calculation: assuming the expected proportion of patients with at least one serious/not serious adverse event surely or possibly related to JPS will be 3 %, and assuming the worst case of each patient contributing for only one JPS implant case: 30 subjects was calculated to be the sample size of this study so that the upper limit of the 95 % confidence interval for the primary endpoint, based on the exact binomial method, is under 15 %. Considering that one patient can contribute for one JPS implant, and considering a 10% drop out rate, the site can enroll a maximum of 40 JPS implant cases.

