6. STUDY OBJECTIVES

6.1 Primary Objective

The primary objective of the study is to evaluate the safety profile of JPS within the scope of its intended purpose, when used according to the manufacturer IFU on a representative population of subjects and users.

In order to fulfill this objective, the safety profile of JPS will be assessed by the following endpoints:

- percentage (%) of subjects with at least one serious/not serious adverse event certainly related or possibly related to JPS (primary endpoint) at device removal follow-up (up to 18 months according to site's standard practice);
- percentage (%) of Medical Device Deficiencies (MDDs) at device removal follow-up (up to 18 months according to site's standard practice).

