10.2 Description Event by Event

10.2.1 V0: Screening and Baseline

Prospective patients who meet the eligibility criteria will be enrolled in the study. Patients who agree to enter the study must sign the approved Informed Consent Form. Consented patients will have performed assessments as outlined in this protocol.

During the screening the investigator will evaluate the eligibility of the patients, checking all inclusion and exclusion criteria. Only those patients who meet all inclusion and exclusion criteria will be enrolled in the study. For each JPS implant a unique case number will be assigned (ID), and reported in the eCRF. Considering that each patient can contribute for more than one JPS implant: one patient can have more than one ID. In the eCRF the IDs are linked to the first ID assigned to the same patient by the clinical site. The patients not enrolled for non compliance will be considered as screening failures and will not be entered in the eCRF. Only for the enrolled patient, the Investigator will collect the demographic data and the medical history of the patient including information concerning the limb to be treated with JPS (baseline) such as the radiographic images and clinical examination.

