12. STATISTICS

12.1 Hypothesis

Hypothesis to test:

the observed primary safety endpoint for JPS ranges within the state-of-art (SOA) safety profile of equivalent plating systems.

State of art:

The proportion of subjects with serious/not serious adverse event surely or possibly related to the device reported in the scientific literature for the treatment of congenital deformities and fractures in lower limb of pediatric patients by the means of equivalent plating systems is between 5.1 % and 15.0 % depending on many factors, mainly the diversity of the primary diagnosis.

Assumption:

for the sole purpose of the sample size calculation, it was required to assume an expected proportion for the primary safety endpoint of JPS. The sample size, therefore, was calculated estimating the required number of subjects (considering the case the each patient contributes for only one JPS implant) so that the upper limit of the 95 % confidence interval for the expected proportion is ranged within the SOA (i.e. 95 % CI upper limit \leq 15 %).

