12.2 Sample size calculation

Assuming the expected proportion of patients with at least one serious/not serious adverse event surely or possibly related to JPS will be 3 %, 30 subjects (considering the case the each patient contributes for only one JPS implant) was calculated to be the sample size of this study so that the upper limit of the 95 % confidence interval for the primary endpoint, based on the exact binomial method, is under 15 %.

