12.3.2 Safety Variables

The safety profile of JPS will be assessed by the following safety endpoints:

- percentage (%) of subjects (\pm the upper and lower of limit of the 95 % confidence interval) with at least one serious/not serious adverse event surely or possibly related to

JPS (ADEs) (primary safety endpoint). Exact limits will be calculated by Chi-square test with Clopper option.

- percentage (%) of medical device deficiency (secondary safety endpoint). Exact limits will be calculated by Chi-square test with Clopper option.
- percentage (%) of implants where a serious/not serious adverse event certainly related or possibly related to JPS is registered on total surgical implants performed (up to 18 months according to site's standard practice). Exact limits will be calculated by Chi-square test with Clopper option.

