12.5 Interim Analysis

An interim analysis, not planned at the start of the study, will be performed after at least 20 subjects will be enrolled and completed the "Bone Consolidation" event.

The aim of this interim analysis is to verify the consistency of testing hypothesis and to confirm the historical data on the medical device safety and performance. Interim results will be used to prepare the Clinical Evaluation Report (CER).

To preserve the integrity of the study results interpretation, a correction for multiplicity due to two planned analyses (interim+final) will be implemented using the approach proposed by O'Brian-Fleming for sequential design. (*Shein –Chung Chow et Al Sample size calculations in Clinical Research 2003, Christopher Jennison et Al Group Sequential Methods with applications to clinical Trials, 2000*)

For this purpose, sample size will be recalculated using this approach (all details are reported in the cited bibliography):

- The initial sample size will be correct by factor 1.008 for a two-sided test at 5% level and 80% power. The final sample size is $30*1.008=30.2$
- The probability level will be correct by factor 1.977, at interim the P value will be 0.0052 while at the final analysis P value will be 0.048. The corresponding confidence limits will at interim 99.5% and at final analysis 95.2%

In conclusion, applying the O'Brian-Fleming approach to control the type I error no great impact on sample size is observed and integrity of clinical study is preserved from any interpretation bias.

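### Recruitment is set in implant cases (minimum 30, cap 40) but the primary endpoint and N = 30 are in subjects, so meeting the case minimum does not ensure 30 subjects

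*Protocol*

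**What the plan says.** **Recruitment is in implants.** The Procedures row of the protocol synopsis allows at most 40 implant cases, predicts 10 % dropout, and says these "will contribute for at least 30 cases treated by JPS (note that some patients may contribute for more than one JPS case". Protocol 10.2.1 gives each implant its own ID, so "one patient can have more than one ID".

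**The endpoint and the sample size are in subjects.** Protocol 6.1 defines the primary endpoint as "percentage (%) of subjects with at least one serious/not serious adverse event certainly related or possibly related to JPS (primary endpoint"). Protocol 12.2 states "30 subjects (considering the case the each patient contributes for only one JPS implant) was calculated to be the sample size". An implant-level event rate is listed separately in Protocol 12.3.2: "percentage (%) of implants where a serious/not serious adverse event certainly related or possibly related to JPS is registered on total surgical implants performed". The interim trigger in Protocol 12.5 is also in subjects: the analysis "will be performed after at least 20 subjects will be enrolled and completed" the bone consolidation event.

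**The link between the two units is unclear.** The synopsis statistics row, repeated in SAP section 9, reads "assuming the worst case of each patient contributing for only one JPS implant case: 30 subjects was calculated to be the sample size". Protocol 12.1 drops the worst-case label and says only "considering the case the each patient contributes for only one JPS implant". The synopsis and SAP section 9 then attribute the 40-case cap to 10 % dropout and to a clause on implants per patient. That clause is garbled in both places. As printed, the protocol has a patient contributing one implant; the most plausible reading is more than one, as in Protocol 10.2.1 and 13.3.

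SAP section 13 defines evaluability for implants only. SAP 16.3, 23.1 and 23.1.3 nevertheless plan the number of implants per patient and by-patient adverse event results with exact intervals.

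**The concern.** The width of the primary interval depends on the number of unique subjects. The only numerical recruitment rule is counted in implants, and no limit or expected value is given for implants per patient. The site could therefore satisfy the rule with fewer than the 30 subjects on which the precision statement rests. The worst-case label adds to the problem, because it suggests that further implants in a patient could only help. If subjects were fixed and implants were the target, that would be so. With implants capped, each additional implant in the same patient uses a place that a new subject could have filled.

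**Working it through.** **Inputs.** Minimum 30 cases, cap 40 cases, dropout 10 % (synopsis, Procedures). Expected event rate 3 %, exact 95 % upper limit to be under 15 %, N = 30 subjects (Protocol 12.2). Final intervals are Clopper-Pearson at 95.2 % (SAP section 14). Implants per patient, m, is not given; the values below are assumptions.

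**The plan's own figure.** The Clopper-Pearson upper limit is 1 − (α/2)^(1/n) with zero events, and the (1 − α/2) quantile of Beta(2, n − 1) with one event. With one event in 30, the one-sided 95 % limit is 14.86 %, and 30 is the smallest n under 15 %. The two-sided 95 % limit for the same data is 17.2 %, and 35 subjects are needed (36 at 95.2 %). So N = 30 reproduces only as a one-sided bound. That is a separate matter and is not relied on here.

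**Cases to subjects.** Dropout alone needs 30 / 0.9 = 33.3, so 34 places. The cap leaves 40 × 0.9 = 36 cases. This assumes that dropout leaves m unchanged. Subjects = cases / m, rounded down:

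| m | 30 cases | 36 cases | 40 cases |
|---|---|---|---|
| 1.0 | 30 | 36 | 40 |
| 1.1 | 27 | 32 | 36 |
| 1.2 | 25 | 30 | 33 |
| 1.33 | 22 | 27 | 30 |
| 1.5 | 20 | 24 | 26 |

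Thirty subjects are reached from 30 cases only at m = 1.0, from 36 cases up to 36 / 30 = 1.2, and from 40 cases up to 40 / 30 = 1.33.

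**Subjects to precision.** Two-sided exact upper limits, 95 % / 95.2 %:

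| Subjects | Zero events | One event |
|---|---|---|
| 30 | 11.6 / 11.7 % | 17.2 / 17.4 % |
| 27 | 12.8 / 12.9 % | 19.0 / 19.1 % |
| 25 | 13.7 / 13.9 % | 20.4 / 20.5 % |
| 23 | 14.8 / 14.97 % | 22.0 / 22.1 % |
| 22 | 15.4 / 15.6 % | 22.8 / 23.0 % |
| 20 | 16.8 / 17.0 % | 24.9 / 25.1 % |

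With zero events the limit stays under 15 % down to 23 subjects at both levels. The interim analysis required at least 20 subjects, and SAP section 14 reports it as performed, so lower counts need not be considered. With one event, 30 subjects already exceed 15 %. Measured against 30 subjects, the unit therefore decides whether the criterion can be met only with zero events and 20 to 22 subjects.

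**How far from plan that window is.** Falling below 23 subjects requires m above 30 / 23 = 1.30 at 30 cases, 36 / 23 = 1.57 at 36, or 40 / 23 = 1.74 at 40. With at most two implants per patient, the number of two-implant patients equals cases minus subjects. For 22 subjects that is 8 of 22 (36 %) at 30 cases, 14 of 22 (64 %) at 36 and 18 of 22 (82 %) at 40. Zero events is not a remote outcome at the assumed 3 %: 0.97^30 = 0.40 and 0.97^22 = 0.51.

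**The case against.** The best defence is that the plan does have a subject target and does allow for several implants. The synopsis, Protocol 12.2 and SAP section 9 all give 30 subjects as the sample size. With the garbled clause read as more than one implant, the step from 34 to 40 cases is a deliberate allowance for multiple implants, not accidental slack. This largely stands. A reader might infer that no subject target exists or that the study will fall short of 30; the documents support neither. What remains is that the rule in the Procedures row can be met without reaching the target, and that the allowance runs out at 1.2 implants per patient after dropout.

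A reader might also infer that the worst-case label is simply backwards. The documents do not say worst for what. If it means recruitment burden, one implant per patient is indeed when the most patients are needed to supply the cases. It is the reverse only for subject-level precision under an implant cap.

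On evaluability, the eligibility criteria are written per patient and SAP 16.1 already reports non-evaluable patients with reasons, so the gap in SAP section 13 is small. It is still open how a patient with one evaluable and one non-evaluable implant enters the primary denominator and numerator.

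**Conclusion.** The inconsistency of units holds, and it is minor. Meeting the case minimum ensures 30 subjects only at one implant per patient; the cap does so up to 1.2 after dropout or 1.33 without. The size of any shortfall cannot be stated, because no distribution of implants per patient is given, so the figures are break-points and not estimates. Its effect on the 15 % criterion is narrow, but fewer subjects widen the primary interval whatever the event count.

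The 15 % limit should not be read as a success rule that a shortfall would breach: the plan uses it to derive the sample size, and Protocol 12.4 describes a descriptive analysis. Nor does restoring 30 subjects secure it, given 17.2 % with one event. Nothing here endorses N = 30.

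**What to change.** 1. **Synopsis, Procedures row.** Express the minimum in unique subjects, consistent with the statistics row, Protocol 12.2 and SAP section 9. State that the 40-case cap supports 30 subjects only up to 1.2 implants per patient after dropout.
2. **Synopsis statistics row and SAP section 9.** Correct the garbled clause to say that a patient can contribute more than one JPS implant. Replace the worst-case wording with: assuming one implant per subject; under the 40-case cap, further implants in the same subject reduce the number of subjects.
3. **If enrolment has closed, in place of item 1.** This is likely: last patient in was planned for 2Q 2023 and the SAP was signed in April 2024. State in SAP section 9 the actual number n of unique subjects and the attainable 95.2 % exact upper limits: 1 − 0.024^(1/n) with zero events, and the 97.6 % quantile of Beta(2, n − 1) with one event. For n = 30 these are 11.7 % and 17.4 %; for n = 25, 13.9 % and 20.5 %.
4. **SAP section 13.** State that the by-patient denominator is subjects with at least one evaluable implant, and whether a related event on a non-evaluable implant in such a subject counts.

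The cost is wording in two synopsis rows and two SAP sections. The subject count comes from the IDs already linked per patient in the eCRF and from tables already planned in SAP section 16. No data collection changes. The stated precision may look less favourable.

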4.1 Schematic Diagram

Figure 4.1 Schematic diagram of events related to standard-of-care treatment

Notes: Timelines are estimated as average of the site normal clinical practice.

The term "Visit" and "Event" are used as synonyms to indicate the steps collected by this observational study.

CONFIDENTIAL
Page 12 of 33

5. INTRODUCTION

A manufacturer of a medical device must demonstrate that the intended purpose(s) and claim(s) made in relation to safety and performance of a Medical Device are achieved. As a general rule, such demonstration will require clinical data. Clinical data is data which is relevant to the various aspects of the clinical safety and performance of the device. This may include data from prospective and retrospective clinical investigations of the device concerned as well as market experience of the same or equivalent devices and medical procedures and information from the scientific literature.

The aim of the present study is to collect post-market clinical evidence (post-market clinical follow up - PMCF) on the use of the medical device JuniOrtho Plating System (JPS).

5.1 Background Information

Principles of bone fixation through plating systems

Plating systems are treatment options for bone fixation, indeed they are intended to provide bone fragments stabilization in case of bone fracture or osteotomy. Fixation works by blocking movements that would prevent the normal biological process of callus formation and consolidation. Excessive movement would otherwise increase the incidence of delayed union or nonunion. The very same principle is exploited when surgical fusion of bone fragments is sought, for example in joint arthrodesis or after surgical osteotomies performed to correct a limb deformity.

The JPS is a complete plating system designed to address the specific demands of advanced deformity and trauma reconstruction of the lower extremities in pediatric population and small stature adults. The system is intended for internal fixation and stabilization of fractures, osteotomies, mal-unions and non-unions of long bones of the lower limb.

Indications (as per IFU)

The JPS is intended for internal fixation and stabilization of fractures, osteotomies, mal-unions and non-unions of long bones of the lower limb.

The JPS is indicated for internal fixation and stabilization of femoral and tibial fractures, osteotomies, mal-unions and non-unions. Indications include:

- Varus, valgus, rotational and/or shortening osteotomies
- Femoral neck and/or peritrochanteric fractures
- Proximal and distal metaphyseal fractures
- Pathological and impending pathological fractures

Use of the JPS JuniOrtho Plating System™ is indicated in pediatric (excluding newborns) and small stature adult patients.

5.2 Rationale of the Clinical Investigation and justification of vulnerable group

Orthofix Srl put the JPS on the European market (2019) by the mean of a pre-market clinical evaluation made under the Medical Device Directive (MDD) requirements that was based on the analysis of the scientific literature of equivalent devices.

This study has been planned as part of the Orthofix Srl post-market active surveillance plan for the collection of data on both the clinical performance and the safety profile of the JPS in a representative population of patients and users.

The rationale of the proposed study is to update and support the pre-market clinical evaluation of the JPS with real-word-evidence clinical data, in order to confirm the benefit/risk ratio of this medical device and to keep the CE mark under Medical Device Regulation (MDR) requirements.

The uniqueness of the pediatric population manifests itself in specific indications for lower extremity reconstruction, mostly due to congenital deformities or conditions; different approach in compliance with postoperative care or need for adaptability to rapid growth and development. The JuniOrtho™ Plating System™ (JPS) is a well established, marketed device, commercially available and used as standard device in orthopedic surgeries.

The post-marketing, retrospective/prospective study with CE-marked device JuniOrtho™ Plating System™ (JPS) is designed for gathering real-world medical data from treatment of congenital deformities and fractures in lower limb of pediatric and in small stature adult patients.

All data will be collected from standard medical documentation of patients who have already been treated with JPS. Additionally, all procedures that patients underwent are justified by standard of care.

Constant identification of serious or unexpected serious risk related to the use of the device, especially in real-world experience may bring additional data, that can contribute to the safety of future patients.

In conclusion, patients will not directly benefit from the participation in this study but no additional risk related to the study participation is to be recognized.

